2.8 Safety analyses

For all analyses in this section, the safety set will be used, if not specified otherwise.

2.8.1 Adverse events (AEs)

Adverse events (AEs) will be coded based on the latest available MedDRA version practically possible (version 23.0 or above) that gives preferred term (PT) and primary system organ class (SOC) information. The MedDRA version will be displayed in the respective output footnotes. AEs will be graded using the common toxicity criteria for adverse events (CTCAE) version 5.0. The number (and percentage) of patients with treatment-emergent

- Treatment emergent AEs (TEAEs)
- Serious adverse events (SAEs)
- AEs of Special Interest (AESIs; see [Section 2.8.1.1](#))

will be summarized by:

- treatment, SOC and PT;
- treatment, SOC, PT, and CTCAE grade; and,
- treatment, Standardized MedDRA Query (SMQ) and PT.

In addition, the following events will be summarized by treatment, SOC and PT as well as by SOC, PT and maximum CTCAE grade:

- TEAEs leading to discontinuation of study drug;
- and,
- TEAEs suspected to be study drug related.

Deaths will be summarized by SOC and PT.

Dot plots of the most frequent TEAEs of CTCAE grade 3 or higher, and serious TEAEs will be provided.

AEs, SAEs, and AESIs will be listed, treatment emergent events will be flagged.

In AE summaries, the primary SOC will be presented alphabetically and the PTs will be sorted within the primary SOC in descending frequency of the highest ensovibep dose. If a patient reported more than one AE with the same preferred term, the AE with the greatest severity will be presented. If a patient reported more than one AE within the same primary system organ class, the patient will be counted only once with the greatest severity at the SOC level, where applicable. An AE with missing CTCAE grade will be included in 'All grades' of the summary tables only.

AEs and SAEs will be summarized by SOC, PT and ensovibep treatment arms for each treatment-emergent Anti-Drug Antibodies (TE-ADA) status (TE-ADA-, TE-ADA+induced, TE-ADA+boosted, and a combined TE-ADA+). ADA status is assessed at Day 1, 15, 29, 61 and 91. AE will be summarized according to the TE-ADA status at start of the event. For the event start date, the TE-ADA status used will be the TE-ADA status assessed on the date of the event, if available, or on the first assessment after the event start date. If TE-ADA status following the event is not available, the last available TE-ADA status will be used. Percentages will be based on the number of patients with the respective ADA status at any time post-baseline. For more detail regarding TE-ADAs refer to [Section 2.13.1](#).

ADA data will only be partially available at the time of part A primary analysis, therefore adverse event analyses by TE-ADA status will be analyzed only at the time of final lock i.e., day 91 analyses.

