2.1.1.7 On-treatment/Treatment-emergent

If not stated otherwise, all post-baseline measurements will be considered as on-treatment/treatment emergent and included in the analyses.

A treatment-emergent adverse event (TEAE) is defined as any AE that started after the start of study drug infusion. If the AE start date is the same as date of infusion but time is not available for comparison, the AE will be considered to be treatment emergent.

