2.8.1.1 Adverse events of special interest / grouping of AEs

The following events are AEs of Special Interest (AESI) for this study:

- A CTCAE grade 2 or higher (i.e. requiring intervention) of: Infusion site reactions;
- Hypersensitivity reactions (including anaphylaxis, immune complex mediated hypersensitivity, cytokine release syndrome and other hypersensitivity reactions)
- Worsening of COVID-19 disease that is reported as a moderate or severe AE per investigator judgement, with onset within 1 week of study drug administration.
- Liver events requiring follow-up
- Renal events requiring follow-up

The number (and percentage) of patients with each of the AESIs will be summarized for each Part

- by treatment;
- by treatment and maximum CTCAE grade; and,
- and by treatment, primary system organ class, and preferred term.

A listing of AESIs will be provided. AESIs will be analyzed as flagged by the investigator on the eCRF.

Safety topics of interest are defined in the electronic case retrieval sheet (eCRS). These will be summarized for each part

- by safety topic of interest
- by safety topic of interest and preferred term
- by safety topic of interest and preferred term for those AEs marked as AESI by the investigator

AESIs and safety topics of interest will be in addition will be summarized for each treatment-emergent Anti-Drug Antibodies (TE-ADA) status. ADA data will only be partially available at the time of part A primary analysis, therefore this analysis will only be done at the time of final lock i.e., day 91 analyses.

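### The AE-by-ADA percentages sort events by antibody status at onset but divide by everyone who ever had that status, so they can mislead in either direction

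*SAP*

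**What the plan says.** SAP 2.8.1 plans tables of AEs and SAEs for the ensovibep arms by treatment-emergent ADA (TE-ADA) status: negative, induced, boosted and combined positive. Its counting rules are:

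- **Sampling:** "ADA status is assessed at Day 1, 15, 29, 61 and 91".
- **Numerator:** "AE will be summarized according to the TE-ADA status at start of the event".
- **Look-up:** the status used is the one "assessed on the date of the event, if available, or on the first assessment after the event start date". The fallback is: "If TE-ADA status following the event is not available, the last available TE-ADA status will be used".
- **Denominator:** "Percentages will be based on the number of patients with the respective ADA status at any time post-baseline".

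The eligible events are all treatment-emergent AEs, "defined as any AE that started after the start of study drug infusion" (SAP 2.1.1.7). SAP 2.8.1.1 adds that AESIs and safety topics of interest "will be summarized for each treatment-emergent Anti-Drug Antibodies (TE-ADA) status", with no denominator of its own. Both sections defer these tables to the final Day 91 lock. Protocol 12.5.2 asks for AEs and SAEs by TE-ADA status and gives no counting rule.

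**The concern.** The numerator treats status as something that changes over time. The denominator treats it as a label that a patient carries for the whole study. Someone negative at Day 15 and positive at Day 29 is a full member of both denominators, although events up to Day 15 can count only as negative and later ones, if positivity persists, only as positive. The rule sets no at-risk group, patient-time or landmark.

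At stake is the reading of the planned tables that relate antibodies to safety. For Part B, protocol Table 2-1 makes the clinical relevance of immunogenicity, including for safety, a secondary objective. If the Part A rule is reused there, the same artefact goes with it.

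**Working it through.** The plan gives no figure for this table, so there is none to reproduce. I applied its rules to cases in which AE risk is the same whatever the ADA status, so that any gap comes from the counting. From the SAP: sampling days, look-up rule and denominator rule. Assumed: AE timing, conversion pattern, positivity that persists, and no dropout.

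**Simple example.** 24% of patients have an AE before Day 15 and another 6% after it; 30% are first positive at Day 29. Everyone is negative at Day 15, so the negative denominator is 1.

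- TE-ADA-: (0.24 + 0.06 × 0.70) / 1 = 28.2%
- TE-ADA+: (0.06 × 0.30) / 0.30 = 6.0%

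The true risk is 30% for all. If instead 10% are positive at Day 15 and a further 20% at Day 29:

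- TE-ADA-: (0.24 × 0.90 + 0.06 × 0.70) / 0.90 = 0.258 / 0.90 = 28.7%
- TE-ADA+: (0.24 × 0.10 + 0.06 × 0.30) / 0.30 = 0.042 / 0.30 = 14.0%

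**Fuller example.** The risk of any AE by Day 91 is 40% for all, a cumulative hazard of -ln(0.60) = 0.511, split 60/20/12/8% over the four sampling intervals. First positive at Day 15/29/61/91: 5/15/15/5%; never: 60%. For patients who spend a share s of the hazard in a status, the chance of an event there is 1 - exp(-0.511s).

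- TE-ADA-: (0.15 × 0.264 + 0.15 × 0.335 + 0.05 × 0.375 + 0.60 × 0.400) / 0.95 = 0.3487 / 0.95 = 36.7%
- TE-ADA+: (0.05 × 0.400 + 0.15 × 0.185 + 0.15 × 0.097 + 0.05 × 0.040) / 0.40 = 0.0643 / 0.40 = 16.1%

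The denominators add to 0.95 + 0.40 = 135% of patients. The apparent reduction is 1 - 16.1/36.7 = 56%, where the true one is zero.

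**Range.** True risk is 40% in every row. The first two rows are closed form; the others are simulated with 400,000 patients.

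| First positive at Day 15/29/61/91 (%) | AE hazard by interval (%) | TE-ADA- | TE-ADA+ |
|---|---|---|---|
| 5/15/15/5 | 60/20/12/8 | 36.7% | 16.1% |
| 5/15/15/5 | constant per day | 30.3% | 31.2% |
| 20/10/5/5 | 60/20/12/8 | 37.7% | 26.5% |
| 2/4/3/1 | 60/20/12/8 | 39.2% | 18.4% |
| 0/5/20/15 | 80/10/6/4 | 38.9% | 4.4% |
| 10/25/25/10 | constant per day | 22.8% | 31.1% |
| 40/0/0/0 | constant per day | 40.1% | 40.1% |

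**An early AESI.** COVID-19 worsening counts as an AESI only with onset within a week of dosing. Given a Day 15 sample, every such event takes the Day 15 status. With true risk r and the fuller example's conversion pattern, and if the 2.8.1 denominator carries over, TE-ADA- shows r and TE-ADA+ shows r × 5/40 = 0.125r.

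**Does dividing by patient-time cure it?** In the simple example, spread the later 6% evenly over Days 15 to 91 (76 days) and switch status at Day 29. Negative time per patient is 0.70 × 90 + 0.30 × 28 = 71.4 days; positive time is 0.30 × 62 = 18.6 days. Positive events are 0.06 × (62/76) × 0.30 = 0.0147; negative events are 0.30 - 0.0147 = 0.285. The rates are 0.120 and 0.024 per 30 patient-days, a ratio of about 5.1 against 28.2/6.0 = 4.7 in the planned table. In the fuller example pooled rates are 0.207 (negative) and 0.083 (positive). Pooling works only under a constant hazard (0.170 in both).

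**What does remove the gap?**

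- Ever against never positive, AEs after the Day 15 sample, simple example: 0.06 × 0.30 / 0.30 = 6.0% and 0.06 × 0.70 / 0.70 = 6.0%.
- Status at event with an at-risk denominator within each interval, fuller example (positive, negative): 26.3, 26.4%; 9.7, 9.7%; 5.9, 6.0%; 4.1, 4.0%.

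**The case against.** The strongest reply is that this is a descriptive, untested table with limited reach, and that the size and sign of any distortion are unknown. Much of that stands.

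- **Dose selection.** Because protocol 12.4.2 names ADAs among the safety endpoints for choosing the Part B dose, a reader might infer that this table feeds that choice. The documents do not support it: ADAs enter there only as available, and SAP 2.8.1 schedules the AE-by-ADA analyses for the final Day 91 lock only, after the primary analysis on which the dose is chosen.
- **Direction.** A reader might infer that the rule always makes antibody-positive patients look safer. It does so when AEs cluster early and conversion is later; the constant-hazard rows show near-equality and a reversal.
- **Hidden reactions.** A reader might infer that antibody-related reactions would be concealed. AEs, SAEs and AESIs are also listed and summarised by treatment arm, placebo included, so the events stay visible. Only their relation to ADA status is blurred.
- **Part B.** The SAP gives only an outline for Part B and leaves detail to a later amendment, so the rule is not yet fixed there.
- **Unseen text.** SAP 2.8.1 refers to Section 2.13.1 for TE-ADA detail, which is not in the released text, so whether positivity persists once seen cannot be checked. But the denominator rule is stated in full in 2.8.1, and classifying by status at event start presupposes that status can change.

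None of this reconciles the numerator with the denominator.

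**Conclusion.** The rule is wrong as written. Whenever status changes between post-baseline samples, the percentages describe no defined group of patients and can differ with no antibody effect. The mismatch follows from the SAP wording alone; its size does not. The 28.2% against 6.0%, the 36.7% against 16.1% and the reversed 22.8% against 31.1% all rest on assumed AE timing and conversion. The cause is not only ignored time at risk: early AEs are set against later positivity, which is why pooled patient-time fails.

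It bears on the AE and SAE tables by TE-ADA status, on the AESI and safety-topic tables if they inherit the denominator, and on Part B if the rule is reused. The primary analysis is untouched.

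Two smaller faults come from the look-up rule. An event just after Day 29 in a patient first positive at Day 61 counts as positive up to 32 days before positivity was seen. And a patient with an AE but no post-baseline ADA sample could enter a numerator through Day 1 status while being in no denominator.

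**What to change.** Replace the denominator rule in SAP 2.8.1 with one of these, and state in 2.8.1.1 that it applies there too:

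1. **One status per patient** in numerator and denominator (ever against never TE-ADA positive), restricted to AEs starting after the first post-baseline ADA sample. Note that patients who leave early have less chance to become positive, so some bias from dropout can remain.
2. **Status at event, by interval.** Keep the event rule, but divide by patients or patient-time at risk in that status within Days 1-15, 15-29, 29-61 and 61-91, assigning status to the denominator by the same look-up as for events.

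Do not use pooled patient-time without the interval split. State how patients with no post-baseline ADA sample are handled, and carry the chosen rule into the Part B SAP amendment.

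The cost is a SAP wording change and modest reprogramming of one set of safety tables due at the Day 91 lock. The data are already collected, and since protocol 12.5.2 sets no counting rule, no protocol amendment is needed.

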2.8.1.1 Adverse events of special interest / grouping of AEs

The following events are AEs of Special Interest (AESI) for this study:

- A CTCAE grade 2 or higher (i.e. requiring intervention) of: Infusion site reactions;
- Hypersensitivity reactions (including anaphylaxis, immune complex mediated hypersensitivity, cytokine release syndrome and other hypersensitivity reactions)
- Worsening of COVID-19 disease that is reported as a moderate or severe AE per investigator judgement, with onset within 1 week of study drug administration.
- Liver events requiring follow-up
- Renal events requiring follow-up

The number (and percentage) of patients with each of the AESIs will be summarized for each Part

- by treatment;
- by treatment and maximum CTCAE grade; and,
- and by treatment, primary system organ class, and preferred term.

A listing of AESIs will be provided. AESIs will be analyzed as flagged by the investigator on the eCRF.

Safety topics of interest are defined in the electronic case retrieval sheet (eCRS). These will be summarized for each part

- by safety topic of interest
- by safety topic of interest and preferred term
- by safety topic of interest and preferred term for those AEs marked as AESI by the investigator

AESIs and safety topics of interest will be in addition will be summarized for each treatment-emergent Anti-Drug Antibodies (TE-ADA) status. ADA data will only be partially available at the time of part A primary analysis, therefore this analysis will only be done at the time of final lock i.e., day 91 analyses.

2.8.2 Deaths

See [Section 2.8.1](#). A listing will be provided for all deaths by treatment for each Part.

2.8.3 Laboratory data

Laboratory data include measurements of all parameters below:

Test Category	Test Name
Hematology	Hematocrit, Hemoglobin, Platelets, Red blood cells, White blood cells, Differential (Basophils, Eosinophils, Lymphocytes, Monocytes, Neutrophils, Other)
Chemistry	Albumin, Alkaline phosphatase, ALT, AST, Gamma-glutamyl-transferase (GGT), Lactate dehydrogenase (LDH), Bicarbonate, Calcium, Magnesium, Phosphorus, Chloride, Sodium, Potassium, Creatinine, Creatine kinase, Direct Bilirubin, Total Bilirubin, Total Protein, Blood Urea Nitrogen (BUN) or Urea, Uric Acid, Amylase, Lipase, Glucose (non-fasting), CRP, D-Dimer, Ferritin
Coagulation	Prothrombin time (PT), International normalized ratio [INR], Activated partial thromboplastin time (APTT)
Pregnancy Test	Serum / Urine pregnancy test

Clinically notable abnormalities and abnormalities in liver function tests (LFT) are described in [Section 5.5](#).

Absolute values and change from baseline will be summarized for continuous laboratory parameters by treatment and scheduled visit, including the worst post-baseline value. The direction of interest for worst post-baseline value for selected hematology and biochemistry parameters is shown in [Section 5.4](#).

For selected laboratory tests, the number and percentage of patients with newly occurring or worsening laboratory abnormalities meeting the clinically notable criteria at any time post-

baseline, considering all post-baseline data from scheduled, unscheduled and premature discontinuation visits, will be summarized by treatment and laboratory parameter.

Furthermore, the number and percentage of patients with newly occurring or worsening abnormalities in liver function tests (LFT) will be summarized by treatment and at any time post-baseline considering all post-baseline data from scheduled, unscheduled and premature discontinuation visit.

The number (%) of patients with newly occurring or worsening of notable laboratory values will be provided.

Shift tables using the low/normal/high/ (low and high) classification will be used to compare baseline to the worst post-baseline value.

Listing of all laboratory data of patients with notable abnormal laboratory values will be provided with the classifications relative to the laboratory normal ranges.

Urine pregnancy test data will be summarized using frequency and percentage by treatment. A listing of all pregnancy test data will be provided.

2.8.4 Other safety data

2.8.4.1 Vital signs

Vital signs variables include measurements of systolic and diastolic blood pressure, heart rate, body temperature, respiratory rate, oximetry and weight. Clinically notable abnormalities are described in [Section 5.6](#).

Absolute values and change from baseline will be summarized for all vital signs parameter by treatment and scheduled visit.

For selected vital sign parameter, the number and percentage of patients with newly occurring or worsening abnormalities meeting the clinically notable criteria at any time post-baseline, considering all post-baseline data from scheduled, unscheduled and premature discontinuation visits, will be summarized by treatment and parameter.

A listing of all vital signs of patients with notable abnormal vital signs values (with clinically notable abnormalities being flagged) will be generated.

2.9 Pharmacokinetic endpoints

For all analyses in this section, the PK analysis set will be used.

The PK analysis is specified as a secondary objective in Part A

Free (ensovibep not bound to target) and total (sum of ensovibep not bound and ensovibep bound to target) concentration in serum will be summarized by treatment in each Part at Day 1 pre-dose, Day 1 post-dose (at minute 15 and minute 90), Day 3, Day 8, Day 15, Day 29, Day 61 and Day 91, including the frequency (n, %) of concentrations below the LLOQ and reported as zero. Median concentrations and median log(concentration) over scheduled time-points will be presented graphically by treatment group.

The following PK parameters will be determined: C_{max} , T_{max} , AUC_{last} , AUC_{inf} , $T_{1/2}$, λ_z , V_z , CL . PK parameters will be summarized by treatment in each Part and will include mean (arithmetic and geometric), SD, and CV (arithmetic and geometric), median, minimum, and maximum. The maximum concentration or peak after a dose administration (C_{max}) and the area under the concentration versus time curve (AUC) will be provided.

In addition, population PK modeling will be performed and data from other clinical studies may be pooled. If performed, results of the population PK modeling may be reported separately and will not be part of the CSR.

[REDACTED]

[REDACTED]

[REDACTED]

2.11 Patient-reported outcomes (PRO)

Answers to Short Form 36 Health Survey (SF-36), FDA-recommended 14-symptom [REDACTED] will be reported in each Part. The FDA-recommended 14-symptom questionnaire is described as secondary efficacy objective in Section 2.7.

2.11.1 SF-36

The analysis of SF-36 is specified [REDACTED] a secondary objective in Part B.

In each Part, SF-36 version 1 domain scores, Physical Component Summary (PCS) and Mental Component Summary (MCS), will be summarized by treatment on Days 29, 60 and 91.

Between treatment differences in SF-36v1® summary scores will be analyzed using repeated measures analysis of covariance (ANCOVA) including terms of treatment, baseline risk of progression to severe COVID-19 and/or hospitalization (“high risk” vs. “not at high risk”) visit, and treatment*visit interaction and will include covariates for presence of SARS-CoV-2 antibodies (Yes vs. No) and Geographical region (North America, Europe, Africa, Asia).

Estimated treatment differences at visit and corresponding 95% CI will be tabulated and presented graphically.

In addition a descriptive summary by visit and treatment group will be provided.

SF-36 will be assessed at visit Day 29, Day 61 and Day 91 therefore the repeated measure ANCOVA will be performed only at the time of final lock i.e., day 91 analyses.

[REDACTED]

[REDACTED]

[REDACTED]

2.12 Biomarkers

2.12.2 SARS-CoV-2 antibodies

To assess the effect of ensovibep, compared to placebo, on the occurrence of anti-SARS-CoV-2 antibodies (IgG and IgM), the number (and percentage) of patients with anti-SARS-CoV-2 antibodies at Day 91 will be summarized by treatment.

Neutralizing SARS-CoV-2 antibodies may be summarized descriptively at time of final lock i.e., day 91 analyses. Neutralizing SARS-CoV-2 antibodies data will not be available at the time of part A primary analysis.

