#### **5.2 Exclusion criteria**

Patients meeting **any** of the following criteria are **not** eligible for inclusion in this study.

1. Requiring hospitalization at time of screening, or at time of study drug administration.
2. Oxygen saturation ( $\text{SpO}_2$ )  $\leq$  93% on room air at sea level or ratio of arterial oxygen partial pressure ( $\text{PaO}_2$  in mmHg) to fractional inspired oxygen ( $\text{FiO}_2$ )  $<$  300, respiratory rate  $\geq$  30 per minute, and heart rate  $\geq$  125 per minute.

**In India**, patients with a respiratory rate  $\geq$  24 per minute or with an oxygen saturation  $\leq$  93% on room air ( $\text{SpO}_2$ ) are not eligible.

3. Known allergies to any of the components used in the formulation of the ensovibep or placebo.
4. Suspected or proven serious, active bacterial, fungal, viral, or other infection (besides SARS-CoV-2) that in the opinion of the investigator could constitute a risk when taking intervention.
5. Any serious concomitant systemic disease, condition or disorder that, in the opinion of the investigator, should preclude participation in this study.\*
6. Any co-morbidity requiring surgery within 7 days of dosing, or that is considered life--threatening within 29 days of dosing.
7. Prior or concurrent use of any medication for treatment of COVID-19, including antiviral agents, convalescent serum, or anti-viral antibodies. Purely symptomatic therapies (e.g., over-the-counter [OTC] cough medications, acetaminophen, and nonsteroidal anti-inflammatory drugs [NSAIDs]) are permitted. Prior vaccination for COVID-19 is permitted.
8. Are concurrently enrolled or were enrolled within the last 30 days or within 5 half-lives (whichever is longer) in any other type of medical research judged not to be scientifically or medically compatible with this study.
9. Are pregnant or breast feeding.
10. Women of child-bearing potential, defined as all women physiologically capable of becoming pregnant, unless they are using highly effective methods of contraception at the time of dosing and for 11 weeks after dosing of study drug. Highly effective contraception methods include:
  - a. Total abstinence (when this is in line with the preferred and usual lifestyle of the patient). Periodic abstinence (i.e., calendar, ovulation, symptothermal, and postovulation methods) and withdrawal are not acceptable methods of contraception.

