### **6.2 Other treatments**

#### **6.2.1 Concomitant therapy**

Ongoing long-term medications should be continued and adjusted as needed for the management of underlying conditions.

Symptomatic therapy to manage COVID-19 symptoms, such as antipyretics, analgesics, or oxygen, is permitted. If local standard of care includes further medications tailored to prevent COVID-19 complications (e.g., anticoagulation), these may be used, with the exception of drugs that are immunomodulators (e.g., interferon, tocilizumab, sarilumab, colchicine), immunosuppressives (e.g., steroids) or antivirals. Patients will be required to get upfront approval from the investigator to start any new prescription, OTC, and herbal medication treatments, with the exception of paracetamol up to 3 g/day, which does not require upfront investigator approval.

All medications, procedures, and significant non-drug therapies (including physical therapy and blood transfusions) administered after the patient was enrolled into the study must be recorded on the appropriate Case Report Forms (CRFs). Prior concomitant therapy defined as all medications taken within 30 days prior to enrollment will also be recorded appropriately in the CRFs.

SARS-CoV-2 vaccinations must not be scheduled up to the Day 29 visit, and if possible, should be postponed to take place after completion of the study (Day 91 visit) as ensovibep may neutralize the effectiveness of the vaccine. If such vaccinations take place prior to the last visit, they need to be documented in the relevant electronic Case Report Form (eCRF).

Each concomitant drug must be individually assessed against all exclusion criteria/prohibited medication. If in doubt, the investigator should contact the medical monitor before randomizing a patient or allowing a new medication to be started.

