2.2.1 Subgroup of interest

The following subgroups will be used for the primary variable:

- Subgroups:
 - Risk for COVID-19 disease progression (“high-risk”, “not at high-risk”) – as per protocol
 - Risk for COVID-19 disease progression (“high-risk”, “not at high-risk”) - as per FDA updated definition on May 19, 2021
 - Geographical region (North America, Europe, Africa, Asia)
 - Gender (Male, Female)
 - Age (<55 years, 55-<65 and \geq 65 years)
 - Mutation type (Wild type; Alpha B.1.1.7; Beta B.1.351; Gamma P.1; Delta B.1.617.2; Lambda C.37; Other)*, if available
 - Baseline \log_{10} SARS-CoV-2 viral load (\log_{10} SARS-CoV-2 viral load < 6 , \log_{10} SARS-CoV-2 viral load ≥ 6)
 - SARS-CoV-2 antibodies at baseline (No, Yes)
 - Baseline severity of COVID-19 (mild, moderate)

* List of mutation types may be updated if new variants of concern are detected during the study.

Mutation type data will only be partially available at the time of part A primary analysis, therefore this subgroup will be analyzed at the time of final lock i.e., day 91 analyses only.

Subgroups may need to be combined if there is not a sufficient number of patients (e.g. at least 10%) in a respective subgroup. Regions will only be combined if models fail to converge, whether or not having less than 10%.

For tables presenting results from statistical models, the treatment effects in the subgroup will be derived using an additional covariate as a fixed effect and the appropriate interaction terms in the model, if necessary.

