2.3.2 Background and demographic characteristics

Demographic and other baseline data including disease characteristics will be listed and summarized descriptively by treatment arm for the FAS and SS (if different from the FAS).

Demographics listed below will be summarized:

- Age (years)
- Gender (Male, Female)
- Race (White, Black or African American, Asian, Native Hawaiian or Other Pacific Islander, American Indian or Alaska Native, Multiple, Unknown, Not reported)
- Ethnicity (Hispanic, Non-hispanic)
- Age group (<25 years, 25-<45 years, 45-<65 and \geq 65 years)
- Geographical region (North America, Europe, Africa, Asia)

The following baseline characteristics will be summarized:

- Body weight (kg)
- BMI (kg/m^2), calculated as weight in kg divided by (height in m) 2
- BMI group (<18.5 kg/m^2 , 18.5-<25 kg/m^2 , 25-<35 kg/m^2 , \geq 35 kg/m^2)
- Risk for COVID-19 disease progression (“high-risk”, “not at high-risk”) – as per protocol
- Risk for COVID-19 disease progression (“high-risk”, “not at high-risk”) – as per FDA updated definition on May 19, 2021
- Chronic kidney disease (No, Yes)
- Diabetes mellitus (No, Yes)
- Immunosuppressive disease (No, Yes)
- Currently receiving immunosuppressive treatment (No, Yes)
- \geq 65 years of age (No, Yes)
- \geq 55 years of age and cardiovascular disease, or hypertension, or chronic obstructive pulmonary disease / other chronic respiratory disease (No, Yes)
- Baseline ADA status (ADA+, ADA-)*
- Baseline \log_{10} SARS-CoV-2 viral load (copies per mL)
- Baseline \log_{10} SARS-CoV-2 viral load (\log_{10} SARS-CoV-2 viral load $<$ 6, \log_{10} SARS-CoV-2 viral load \geq 6)

- Mutation type (Wild type; Alpha B.1.1.7; Beta B.1.351; Gamma P.1; Delta B.1.617.2; Lambda C.37; Other)*, if available
- SARS-CoV-2 antibodies as baseline (No, Yes)
- Baseline severity of COVID-19 (mild, moderate, severe (if appears)). Details on definition are included in [Section 5.2](#).

* ADA samples will not be analyzed for Placebo patients, therefore ADA status will be missing for Placebo patients.

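### The Day 91 antibody percentage in SAP 2.12.2 counts patients already positive at baseline, which dilutes any difference between arms; a table in baseline-negative patients should stand beside it

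*SAP*

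**What the plan says.** SAP 2.12.2 gives its aim as "To assess the effect of ensovibep, compared to placebo, on the occurrence of anti-SARS-CoV-2 antibodies (IgG and IgM"). The measure is a count: "the number (and percentage) of patients with anti-SARS-CoV-2 antibodies at Day 91 will be summarized by treatment". The visible text of that section has no restriction or split by baseline antibody status or vaccination. For neutralizing antibodies it says only that "Neutralizing SARS-CoV-2 antibodies may be summarized descriptively at time of final lock i.e., day 91 analyses".

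Baseline antibody status is collected and used in several other places:

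- It is a baseline characteristic (SAP 2.3.2).
- It is a covariate in the primary ANCOVA (SAP 2.5.2 and 5.7.1), in the Cox model for sustained recovery (SAP 2.7.2.2) and in the SF-36 model (SAP 2.11.1).
- It is on the subgroup list in SAP 2.2.1, but that list is introduced with "The following subgroups will be used for the primary variable", so it does not reach the antibody table.

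On vaccination, Protocol 5.2 states "Prior vaccination for COVID-19 is permitted". Protocol 6.2.1 bars scheduling a vaccination up to Day 29 and asks for postponement beyond Day 91 where possible. It adds: "If such vaccinations take place prior to the last visit, they need to be documented". Protocol 6.2.3 allows convalescent serum or antiviral antibodies as rescue after progression.

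**The concern.** A patient who was antibody-positive before the infusion cannot have become positive because of study treatment. Counting that patient as an occurrence adds the same quantity to every arm and pulls the percentages together. The plan evidently expects such patients, since it adjusts for baseline antibody status in three models. Yet the one table whose subject is antibodies has no baseline reference. The next section, SAP 2.12.3, does summarize soluble biomarkers as changes from baseline.

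The table has no planned test, so readers will judge by the percentages. If ensovibep lowers the rate at which antibody-negative patients become positive, the all-patient figures will show a smaller reduction than the true one, and readers may discount it.

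**Working it through.** The documents give no rate, sample size or power for this endpoint, so there is no planned figure to reproduce. All rates below are assumptions used to show scale.

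**Dilution.** Let s be the share positive at baseline, r their Day 91 positivity, and x the Day 91 positivity among baseline-negative patients.

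- Observed percentage in an arm: s·r + (1 - s)·x.
- Randomization makes s equal between arms in expectation. If r is also equal between arms, the s·r terms cancel and the observed gap is (1 - s) × (x on placebo - x on drug).
- It is not necessary that every baseline-positive patient stays positive, only that the rate is the same in each arm.

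With r = 1 and assumed x of 90% on placebo and 60% on drug:

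| s | Placebo | Drug | Observed gap |
|---|---|---|---|
| 0 | 90% | 60% | 30 points |
| 0.1 | 0.1 + 0.9 × 0.90 = 91% | 0.1 + 0.9 × 0.60 = 64% | 27 points |
| 0.3 | 0.3 + 0.7 × 0.90 = 93% | 0.3 + 0.7 × 0.60 = 72% | 21 points |
| 0.5 | 0.5 + 0.5 × 0.90 = 95% | 0.5 + 0.5 × 0.60 = 80% | 15 points |

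**Is it biased?** With no drug effect, x is equal in the arms and the expected gap is 0 for any s. Chance imbalance in s matters little. With 100 patients per arm (SAP 3.1), the SD of the difference in s is √(2s(1 - s)/100): 5.7 points at s = 0.2, and 6.9 points at s = 0.4 or 0.6. With r = 1, one SD moves the Day 91 gap by SD × (1 - x). That is about 0.3 points (5.7 × 0.05) to 1.4 points (6.9 × 0.20) for x between 95% and 80%.

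**What restriction gains.** The next table gives power for a two-sided 5% comparison of two proportions, with 100 per arm for all patients and 100 × (1 - s) per arm for baseline-negative patients. The SAP plans no such test; this is for scale only.

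| Assumed x, placebo vs drug | s | All patients | Baseline-negative only |
|---|---|---|---|
| 95% vs 85% | 0.2 | 8 points, 55.0% | 10 points, 56.0% |
| 95% vs 85% | 0.6 | 4 points, 30.2% | 10 points, 31.7% |
| 95% vs 75% | 0.4 | 12 points, 84.8% | 20 points, 87.6% |
| 95% vs 75% | 0.6 | 8 points, 66.6% | 20 points, 71.5% |

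Restriction restores the size of the effect but adds only about 1 to 5 points of power, because the smaller denominator offsets most of the gain.

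**The case against.** The strongest case for leaving the section alone has four parts.

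- **The all-patient table is a valid randomized comparison.** It keeps every patient and resembles the treatment-policy handling of later antiviral and antibody treatment in the primary estimands. This stands, and is the reason to keep that table.
- **The purpose is inferred.** The SAP speaks of occurrence, not seroconversion. The exploratory objectives and parts of the biomarker text are redacted, so a seroconversion analysis may exist there. This stands in part. SAP 2.12.2 nevertheless states its own aim and measure, and positivity that precedes dosing is a poor fit to an effect of treatment on occurrence. If the analysis exists elsewhere, a cross-reference would be enough.
- **Baseline-positive patients are not all closed cases.** Baseline status is a single yes/no variable, while the endpoint covers two classes. If yes means either class, a patient positive only for IgM could still become positive for IgG. This stands, and is a reason to show the classes separately where possible.
- **Little hangs on it.** The table is not a primary or listed secondary endpoint, and the visible text of SAP 2.5.2 does not name it among the dose-selection criteria. This stands and limits the weight.

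A reader might go further and infer that vaccinated patients and those given rescue antibodies should be removed from the main table. The documents do not support that. Vaccination after dosing and rescue are both post-randomization events. Rescue follows progression, which the drug is meant to reduce, so removing those patients could unbalance the arms. Protocol 6.2.1 also says ensovibep may interfere with vaccine effectiveness, so positivity after a post-dose vaccination cannot be assumed unrelated to treatment.

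**Conclusion.** The point holds as one of dilution. As written, the Day 91 difference is (1 - s) times the difference among baseline-negative patients: 21 points instead of 30 in the example with s = 0.3. This rests on equal s between arms, which randomization gives in expectation, and on equal Day 91 positivity among baseline-positive patients in each arm, which is an assumption. The value of s is unknown from the documents, so the loss could be small (3 of 30 points at s = 0.1) or substantial (15 of 30 at s = 0.5).

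Two stronger readings should be resisted:

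- A reader might conclude that the endpoint cannot show an effect at all. It can: the gap vanishes only if every patient is positive at baseline.
- A reader might add on-study vaccination and conclude that most of the effect disappears. With a share v of the remaining patients vaccinated and all of them positive at Day 91, the gap is (1 - s)(1 - v) times the true one. At s = 0.5 and v = 0.6, 30 points becomes 0.5 × 0.4 × 30 = 6. Those inputs are chosen, not documented, and they sit badly with the protocol's instruction to postpone vaccination.

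This is a cheap improvement to a descriptive table. It changes interpretation far more than detection.

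**What to change.** In SAP 2.12.2:

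- Add a summary, by treatment, of Day 91 antibody positivity among patients antibody-negative at baseline (seroconversion), and state which assay result defines baseline-negative. Show IgG and IgM separately where the assay allows.
- Keep the all-patient percentage beside it.
- Keep patients in the main comparison regardless of post-dose vaccination or rescue with convalescent serum or antiviral antibodies. Show the result without them only as a sensitivity table, labelled as conditioning on post-randomization events.

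Baseline antibody status is fixed before randomization, so restricting on it preserves the randomized comparison. Baseline status, on-study vaccinations and concomitant medications are already recorded. The cost is SAP wording, one extra table (plus the sensitivity table if wanted) and a smaller denominator: 70 instead of 100 per arm if 30% are positive at baseline.
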